9.4 DATA SOURCES

As described above in [Section 9.2.1](#), all variables will be constructed from the 100% Medicare claims and enrolment data from the U.S. Medicare program for the individuals meeting the sample selection criteria. To allow for a one-year baseline period and one-year follow-up period for all beneficiaries who initiated nintedanib between 10/01/2014 and 12/31/2018, the Medicare will span 10/01/2013 through 12/31/2019.

9.5 STUDY SIZE

This study will use the GBTM technique to adherence pattern. Based on empirical results generated by resampling of population data, the maximum likelihood estimates obtained in group-based trajectory models provide reasonably close estimates of their true population values and have approximately normal distributions, even when estimated with a sample size as small as $n = 500$ ([Loughran and Nagin, 2006](#)). A prior study found 1,464 Medicare

beneficiaries who initiated nintedanib between 10/15/2014 and 12/31/2015 ([Corral, Chang et al., 2020](#)). By covering a longer period with the same data, this study should have a sufficient sample.

9.6 DATA MANAGEMENT

Pursuant to requirements guiding participation in the [REDACTED] [REDACTED] Innovator program, [REDACTED] staff will access the Medicare claims and enrolment data only through the [REDACTED]. As such, [REDACTED] will not directly possess any beneficiary-level [REDACTED] data, and the only data to be downloaded from the [REDACTED] will be summary-level statistics.

[REDACTED] staff will access the [REDACTED] environment via the VMware Horizon Client (or whichever client is mandated by [REDACTED]) from dedicated [REDACTED] computers. All [REDACTED] computers are secured with Microsoft BitLocker (for hard drive encryption at rest), Microsoft Azure Active Directory (to implement local security policies, including password management), BitDefender (anti-virus software), and LoJack (for computer tracking and remote wiping if ever needed).

All data manipulation and analysis will be conducted on the [REDACTED] environment remotely by [REDACTED] staff. Data manipulation and analysis will be conducted using SAS software ([REDACTED]) and Stata software ([REDACTED]).

9.7 DATA ANALYSIS

9.7.1 Main analysis

The objective of the main analysis is to identify the adherence patterns of nintedanib among IPF patients. The unit of analysis will be the individual beneficiary, each of whom will have twelve 30-days time intervals measurements of nintedanib PDC spanning the follow-up period. The 12 PDC values (PDC01–PDC12) will be characterized descriptively with measured of central tendency (mean, median), spread (min, max, interquartile range), and proportions of beneficiaries with PDC in each of 0 to <20%, 20 to <40%, 40 to <60%, 60 to <80%, and 80 to 100%.

GBTM will be used to explore the presence of distinct trajectories based on the change in medication adherence over time. The output of GBTM will include estimated probabilities of cluster membership for each individual and an estimated trajectory curve over time for each cluster. Different models will be used to identify 2 to 5 groups by using either cubic, quadratic, or quartic terms. The final models will be based on Bayesian information criteria, and Nagin's criteria for model adequacy ([Nagin and Odgers, 2010](#)), with consideration given to group size such that the proportion of patients in each group is not less than 5% of the total sample. The output of the final model will give us the estimated average trajectory for each group, as well as the estimated probabilities of membership in each trajectory for each patient. We will decide the number and shapes of trajectories based on both model fit,

ensuring enough class size and clinical usefulness ([Hickson, et al, 2020](#)). An example of using GBTM for assessing medication adherence is provided in [Figure2](#) .

[figure not shown]

Figure 2

GBTM medication adherence example

Two sensitivity analyses will be conducted:

- First, the analysis will be repeated for beneficiaries who have positive PDC in the fourth month. In these models, only data from months 4 through 12 will be used to estimate the GBTMs because PDC01–PDC03 will have been used to condition the estimation sample.
- Second, the GBTMs will be re-estimated using as the outcome continuous PDC (for the same twelve 30-day time intervals) and the beta distribution ([Elmer, Jones and Nagin, 2018](#)).

For each trajectory group identified, the mean PDC and the percent of beneficiaries in that group who discontinued nintedanib will be calculated.

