One alternative is to detect trajectories of adherence over time across patients using group-based trajectory modeling (GBTM) ([Nagin and Odgers, 2010](#)). GBTM has been applied with increasing frequency for this purpose in several conditions (Alhazami et al., 2020; [Bateman et al., 2016](#); [Dillon et al., 2018](#); [Feldman et al., 2018](#); [Franklin et al., 2018](#); [Franklin et al., 2015](#); [Franklin et al., 2013](#); [Hargrove et al., 2017](#); [Juarez et al., 2015](#); [Kim et al., 2017](#); [Li et al., 2014](#); [Lo-Ciganic et al., 2016](#); [MacEwen et al., 2016](#); [Paranjpe et al., 2020](#); [Vadhariya et al., 2019](#); [Wang et al., 2019](#); [Zongo et al., 2019](#)). In most of these studies, monthly PDC was assessed for each patient, and a GBTM was fit on the patient-level sequences of monthly PDC values to identify a best-fitting set of adherence trajectories as well as, for each patient, estimates of the probability of belonging to each trajectory group.

Studies that examine adherence trajectories with GBTMs frequently include analyses of the predictors of patients' membership in trajectory groups. Individual characteristics that have been observed to be related to adherence trajectories include age, race, sex, disease severity, comorbidity burden, educational attainment, and socioeconomic status (Alhazami et al., 2020).

Adherence to nintedanib has been evaluated in a few recent studies in the United States. Recent observational studies of nintedanib and pirfenidone suggest that despite different side-

effect profiles, adherence to and persistence with therapy are similar. Adherence (measured as PDC \geq 80%) of nintedanib during one year has been estimated at 60.5% ([Corral, Chang, et al., 2020](#)), 51% ([Corral, DeYoung, and Kong, 2020](#)), and 71.3% ([Ipatova et al., 2019](#)). No studies to our knowledge have analyzed nintedanib adherence using GBTM or comparable methods nor have any studies assessed predictors of adherence.

Therefore, the objective of this study is to assess nintedanib adherence trajectories using GBTMs and understand characteristics of patients within each trajectory. The results of this study can help providers and payers to better identify adults with IPF who are at high risk of nintedanib non-adherence. The identified non-adherence trajectories may highlight the need for a fit-for-targeted intervention strategy to improve adherence in patients within each trajectory.

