9.3.2 Outcomes**9.3.2.1 Primary outcomes**

The main outcome of this study is adherence trajectories to nintedanib. This study will use the GBTM method to identify trajectories of adherence.

For this purpose, first claim for nintedanib will be identified in the Part D claims file based on the presence of an 11-digit NDC code for nintedanib (00597-0143-60, 00597-0145-60 [[CanMED, 2021](#)]). Nintedanib supply calendars will be constructed for the all twelve 30-day time intervals following the individual’s nintedanib initiation date based on each claim’s service date and days’ supply.

-Supply will be assigned as 1 for each day with positive days’ supply of nintedanib.

-If a patient has multiple prescription claims for nintedanib on the same date, the maximum of days' supply will be calculated across the claims and applied to the supply calendar.

-Stockpiling will be implemented if a patient has prescription claims for nintedanib that overlap. Days' supply for the newer claim will be postponed to the first day after end of the older claim's supply.

-For each 30-day month following the nintedanib initiation date, PDC will be calculated as the sum of days with supply divided by 30.

In this way, we are able to calculate monthly nintedanib proportion of days covered. By using the twelve 30-days PDC values as outcomes in the GBTM, the probabilities that a given individual is in each of the latent clusters will be calculated by the GBTM estimation procedure. GBTMs will be estimated using the Stata plugin `traj` ([Jones and Nagin, 2013](#)).

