9.3.3 Covariates

The index date will be defined as the date of the beneficiary's first Part D claim for nintedanib. The baseline period will consist of the 360 consecutive days ending the day before the index date. The follow-up period will consist of the 360 consecutive days starting with the index date.

Variable	Description
Demographic and socioeconomic characteristics	
Age	Age as of index date in years rounded to the nearest whole number will be calculated based on the difference between the beneficiary's birth date and index date.
Age group	Age group will be a categorical variable for age defined as one of 65–74, 75–84, 85+.
Female	Female will be a binary indicator for whether the beneficiary was female as indicated on the enrollment record covering the index date.
Race	Race will be a categorical variable for the beneficiary's self-reported race/ethnicity taking the categories Non-Hispanic White, Black or African-American, Other, Asian/Pacific Islander, Hispanic, American Indian/Alaska Native, and unknown race from the enrollment record covering the index date.
Census region	Census region will be a categorical variable defined by categorizing the beneficiary's state of residence into Census regions (Northeast, South, Midwest, West) from the enrollment record covering the index date (see tab "T2 STATES" in

Variable	Description
	standalone document “Code_List.xlsx”).
Index year	Index year will be a categorical variable defined as the year of the index date and will take the values, 2014, 2015, 2016, 2017 or 2018.
Social deprivation index	Social deprivation index will be a continuous variable ranging between 0 and 100 representing the Social Deprivation Index for the beneficiary's residential ZIP Code as calculated by the [REDACTED]. Social Deprivation Index “is a composite measure of seven demographic characteristics collected in the American Community Survey (ACS): percent living in poverty, percent with less than 12 years of education, percent single parent household, percent living in rented housing unit, percent living in overcrowded housing unit, percent of households without a car, and percent non-employed adults under 65 years of age.” This version was calculated in 2015 using data from 2015 and updates the original version created by Butler et al. (2013) . Higher values for the Social Deprivation Index indicate more social deprivation.
Clinical characteristics	

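### Does the beta-distribution sensitivity analysis break down because monthly PDC can equal exactly 0 or 1?

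*Combined protocol and SAP*

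**What the plan says.** Section 9.3.2.1 builds a daily supply calendar. The coding rule is "Supply will be assigned as 1 for each day with positive" days' supply. Where fills overlap, "supply for the newer claim will be postponed to the first day after end of the older" claim. For each 30-day month, "PDC will be calculated as the sum of days with supply divided by 30". The main outcome follows directly: "By using the twelve 30-days PDC values as outcomes in the GBTM", the model yields each patient's probabilities of group membership. The same section names the Stata plugin `traj` as the software.

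Section 9.3.3 fixes the clock: "The follow-up period will consist of the 360 consecutive days starting with the index date".

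Section 9.7.1 sets 2 to 5 groups, the polynomial orders, selection by BIC and adequacy criteria, and a minimum group share of 5%. It does not name a distribution for the main model. Its second sensitivity analysis is one in which "the GBTMs will be re-estimated using as the outcome continuous PDC (for the same twelve 30-day time intervals) and the beta distribution", with a citation to a methods paper on the beta distribution in group-based trajectory models. For each group, "the mean PDC and the percent of beneficiaries in that group who discontinued nintedanib will be calculated".

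**The concern.** There are two grounds for worry.

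- **Boundary values.** The beta distribution lives strictly between 0 and 1. A fully supplied month has PDC exactly 1 and an unsupplied month exactly 0. One such month can leave a patient without a finite log-likelihood, and BIC is computed from that likelihood. The plan gives no rule for these months.
- **Unclear contrast.** Section 9.7.1 presents continuous PDC as something the sensitivity run brings in, yet section 9.3.2.1 already uses the PDC values as the main outcome. With the main distribution unnamed, the run might change the distribution, the outcome coding or both.

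This is the plan's only check of the trajectories against another distribution. The study hopes to help providers and payers "better identify adults with IPF who are at high risk of nintedanib non-adherence", so a check in which the early-stopping group appeared or vanished according to an unstated data step would be of little use.

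**Working it through.** The plan gives no figure to reproduce here. The check has five steps.

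**1. Possible values.** PDC = k/30 with k = 0, 1, ..., 30, which is 31 values including 0 and 1. Follow-up starts on the first fill, so a first fill of at least 30 days gives k = 30 and PDC01 = 30/30 = 1.

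**2. Beta density.** With mean m and precision p, the density is proportional to y^(mp − 1) × (1 − y)^((1 − m)p − 1). At y = 1 it is infinite if (1 − m)p < 1 and zero if (1 − m)p > 1; y = 0 behaves likewise with mp. On simulated PDC data the unadjusted log-likelihood was minus infinity for shapes (2, 2) and undefined for shapes (2, 0.5). Some boundary handling is needed.

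**3. How common boundary months are.** The documents do not say. Supply calendars were simulated for 1,500 patients under the section 9.3.2.1 rules. Assumed: 30- or 90-day fills; 20, 50 or 80% of refills late; mean gap 4, 10 or 20 days; stopping hazard 0, 3 or 6% per 30 days. Scenarios were kept if the share with one-year PDC of at least 80% fell within the 51% to 71.3% cited in section 7.

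| Assumed pattern | Months at exactly 0 or 1 |
|---|---|
| 90-day fills | 79–96% |
| 30-day fills, 20 or 50% late | 57–85% |
| 30-day fills, 80% late | 26–45% |

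The share depends on refill behaviour. The plan's rules alone do not make boundary months the majority.

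**4. Ways to make the model run.** A second simulation used 12 cohorts of 1,464 (the count cited in section 9.5). They comprised 3 adherence levels × first fill of 14 or 30 days × 2 seeds. Assumed: later fills of 30 days, 40% of refills 0–4 days early, the rest late by a gamma-distributed gap, a 2% chance per refill of a 20–74-day break, and a gamma-distributed stopping hazard. Models were cubic with 2–5 groups. The best BIC was taken among models with every group at least 5% and mean assignment probability at least 0.70.

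- *Move values inward, all months kept.* For example (29 × PDC + 0.5)/30, so 0 becomes 0.5/30 = 0.017 and 1 becomes 29.5/30 = 0.983. The lowest group held 8–17% of patients with mean PDC 0.07–0.15. Shifts of 0.017, 0.01, 0.001 and 0.00003 agreed with adjusted Rand index 0.76–1.00 under one shared precision, the number of groups changing in 3 of 12 cohorts. With group-specific precision the index was 0.44–0.98.
- *Delete exact 0 and 1 months.* Between 6.5% and 22% of patients kept no value and no early-stopping group appeared. Agreement with the inward shift was 0.01–0.11. In 6 of 12 cohorts no model met the selection limits, and a two-group fit had to stand in.

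The second route conflicts with the text: section 9.7.1 specifies the same twelve intervals and gives every beneficiary twelve measurements.

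**5. Readings of the main outcome.** In the same cohorts, a normal model for the PDC fraction put 52–66% in the top group, and a logit model for PDC of at least 80% put 35–44% there (index 0.45–0.56). The lowest group was similar in size: 9–16% against 9–14%. Only the PDC fraction is written down; no section mentions a dichotomised trajectory outcome. The sensitivity run itself, continuous PDC with a beta distribution, is the same under both readings.

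**The case for a change.** The best case for a change is that the choice matters and is cheap to fix in advance. A citation does not settle a boundary rule. The constant affects the fit: in one data set with 57% of months at 0 or 1 and observed mean PDC 0.761, a single beta distribution had log-likelihood 11,679, 31,469 and 90,792 when 0 and 1 were moved inward by 1/60, 0.001 and 0.000001. The fitted means were 0.679, 0.670 and 0.663. Section 9.7.2 also takes membership probabilities from a trajectory model into the predictor analysis, so the choice could carry through.

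Part of this stands. The rule and the main distribution are unstated, and with group-specific precision the classification can move appreciably. The rest weighs less:

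- BIC compares models fitted to the same data under one constant, so the large differences in log-likelihood level between constants do not themselves decide the number of groups.
- The fitted means differ by only 0.679 − 0.663 = 0.016 across the three shifts. All lie 0.08 to 0.10 below the observed mean, which is a property of the beta fit that writing down a constant would not remove. The natural reading of the planned mean PDC per group is the observed mean, which the rescaling does not touch.
- Any constant written in now would be arbitrary. A model with point mass at 0 and 1 would be equally defensible.
- The top-group difference in step 5 concerns the main model, and it needs a dichotomised outcome that has to be inferred from the single word continuous.

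**Conclusion.** No change to the plan follows. An ordinary beta likelihood needs a boundary rule, section 9.7.1 does not state one, and the main model's distribution is unnamed. These are missing details that analysts must settle to obtain any fit, and the text steers them to a sensible choice: PDC values as the outcome, all twelve intervals kept, a cited beta method and named software. Whether that method or software already handles 0 and 1 cannot be checked from the documents.

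Among inward shifts with a shared precision, agreement was 0.76–1.00. The striking disagreement (0.01–0.11) arises only if boundary months are deleted, which does not fit the plan. These sizes rest on assumed refill patterns and are illustrative. The matter touches one supporting analysis. Once the main model has been fitted and its distribution reported, a reader can see what the beta run changes. Naming the boundary handling and the precision structure in the study report is ordinary good practice and is enough.

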9.7.2 Additional analysis

The objective of the additional analysis is to understand characteristics of patients within each nintedanib adherence trajectory among IPF patients. The unit of analysis will be the individual beneficiary, and the outcomes will be the vector of estimated probabilities of

cluster membership from a given GBTM. The predictor variables will be the baseline covariates ([Section 9.3.3](#)).

The distributions of the covariates will be characterized with descriptive statistics, including frequencies and percentages for discrete or categorical variables, and means, standard deviations, medians, and interquartile ranges for continuous variables.

Associations between the predictors and the probabilities of trajectory membership will be quantified using fractional multinomial logit models estimated via quasi-maximum likelihood ([Papke and Wooldridge, 1996](#)). Associations will be calculated both as odds ratios (exponentiating the fractional multinomial logit model's coefficients) and average marginal effects on the probability scale.

9.8 QUALITY CONTROL

The Medicare administrative data collection occurred in the past and the data will be obtained from [REDACTED]. No additional insight into the data collection procedures is available beyond that which has been published by [REDACTED]. As a result, we are relying on quality control measures implemented by [REDACTED] during data collection.

[REDACTED] has established protocols for quality control of analyses. All analyses are audited before the finalization of results. The auditor will independently review the conceptual and technical elements of the analysis with a critical eye to identifying any flaws or potential errors.

The auditor will understand the goal of the analysis and the expected results, and then review each step of the [REDACTED] data analysis audit checklist (available upon request). The auditor will keep a list of questions or issues and then meet with the project lead to discuss any findings. If errors or issues are found that change the results, the auditor will perform an incremental audit to ensure that changes have been implemented properly and any change in results aligns with expectations about magnitude and direction.

9.9 LIMITATIONS OF THE RESEARCH METHODS

This study has several limitations, which include:

- Absence of data on some behavioral factors (e.g. patient-physician communication, fear of disease/side effects, and family support) which may affect non-adherence.
- Reliance on prescription fill data to define adherence may not capture the actual use of the medication.
- In this study, patients who had 12 months of continued fee-for-service enrollment of Parts A, B, and D before and after index dates were included.

9.10 OTHER ASPECTS

9.10.1 Data quality assurance

The following quality assurance and quality control measures will be applied to all programming that executes data extraction and transformation by [REDACTED]:

- Check program logs for notes, warning messages, and errors
- Check derived data values against source data for a patient sample to ensure correct derivation
- Verify that variables needed to support tables/listings/figures/ are found in the derived data set
- Check that data fields are not truncated
- Check data points for values outside expected ranges, where appropriate
- Check that data are rounded correctly and in accordance to the analysis plan
- Check that abbreviations, range categories, and subgroups conform to the analysis plan
- Ensure the consistency of sample counts across relevant tables/listings/figures
- Check formats consistent with the analysis plan
- Ensure no typos, misspellings, or false values
- Check that summary statistics are correct; check at least one category in each summary table against the data listings
- Check that data are in accordance with the Data Plan
- Check that subgroups conform to the Data Plan
- Ensure there are no duplicate observations

9.10.2 Study records

Not applicable

10. PROTECTION OF HUMAN SUBJECTS

Not applicable based on secondary use of data without access to identifiable patient data.

10.1 STUDY APPROVAL, PATIENT INFORMATION, AND INFORMED CONSENT

Not applicable to this study.

10.2 STATEMENT OF CONFIDENTIALITY

Not applicable to this study

11. MANAGEMENT AND REPORTING OF ADVERSE EVENTS/ADVERSE REACTIONS

Given the information available within the Medicare claims database for this study, extraction on adverse events data will not be conducted and only data related to the study objectives will be extracted. Therefore, information about individual adverse events will not be available. Only data on aggregate-level medication use will be analysed.

